2. PROTOCOL SUMMARY

2.1 Study design and conduct

This is a local, prospective, multicentre, non-interventional, observational study in adult patients with T2DM diagnosis.

Due to the observational design, patient visits to the referring physician are not pre-specified by the study protocol, but will follow usual clinical practice. All patient-care decisions, including diagnostic and therapeutic interventions, will be made by and conducted at the discretion of the participating study physicians according to their clinical judgment and the local standard of medical care.

[figure not shown]
Start of the study is defined as the date of the start of data collection (first patient signed ICF for data collection).

End of the enrolment (Last Patient First Visit) is defined as the date when the last patient signs ICF and enrolled in the study.

End of the patient observation (Last Patient Last Visit) is defined as the last date when the patients are observed in the scope of the study.

End of study (end of data collection) is defined as the date when the last data point is collected. Up to this date all the CRFs should be completed and all the data clarifications (queries) should be done.

The study is considered to be completed after the database is closed, the final statistical analysis is performed and the study report is written. The study report must be signed within 12 months after the collection of the last data point.

It's planned that interim statistical analysis of study data will be performed as soon as 350 first study patients have completed the study by achieving final study visit or discontinuing their participation.

Term	Baseline visit (V1)	Observational visit (V2)	Final visit (V3)
Inclusion/exclusion criteria	X		
Signed Informed consent form	X		
Date of visit	X	X	X
Demographic information	X		
Medical history including history of DM2T	X		
Concurrent medical conditions	X		
Physical examination and vital signs*	X	X	X
Study medication	X	X	X
Laboratory tests and instrumental exams*	X	X	X
Concomitant treatment (including DM2T treatment)	X	X	X
Healthcare resources utilization		X	X
Adverse events		X	X

For study details and study assessment's schedule see the Protocol of the Study.

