2.4 Sample size and power

Sample size was calculated for the primary objective of the study: to evaluate the effect of Vipidia® on glycosylated hemoglobin (HbA1c) level dynamics in patients with diabetes mellitus type 2 (V3). Sample size was calculated using SAS 9.3 proc power procedure (power for Confidence Interval for Paired Mean Difference as for accuracy of parameter estimation) for following parameters (fixed scenario elements):

Fixed Scenario Elements	
Distribution	Normal
Method	Exact
Correlation	0.35
Nominal Prob(Width)	0.9
Number of Sides	2
Alpha	0.05
Prob Type	Conditio nal

Standard deviation was assessed based on S. Del Prato et. al study and was considered to be at most 0.70% (for glycosylated hemoglobin level dynamics). To determine required number of patients values from 0.60% to 0.70% were taken. Desired half-wide for parameter estimation was set as range between 0.05 – 0.1. Following required number of pairs were calculated:

Computed N Pairs				
Ind ex	Half-Width	Std Dev	Actual Prob(Width)	N Pairs
1	0.05	0.60	0.904	770
2	0.05	0.65	0.904	899
3	0.05	0.70	0.900	1037
4	0.06	0.60	0.904	542
5	0.06	0.65	0.903	632
6	0.06	0.70	0.903	729
7	0.07	0.60	0.906	404
8	0.07	0.65	0.902	470
9	0.07	0.70	0.904	542
10	0.08	0.60	0.902	313
11	0.08	0.65	0.907	365
12	0.08	0.70	0.905	420
13	0.09	0.60	0.905	251
14	0.09	0.65	0.906	292
15	0.09	0.70	0.907	336
16	0.10	0.60	0.904	206
17	0.10	0.65	0.902	239
18	0.10	0.70	0.904	275

For worst-case scenario maximum required number of pairs is 1037. Taking into account a possible dropout of 25%, to reach study objectives in regard to this endpoint, it is recommended to enrol at least 1383 patients into the study.

As well as for the primary objective, sample size was calculated for the secondary objective of the study: to evaluate the effect of Vipidia® on glycosylated hemoglobin (HbA1c) level dynamics in patients with diabetes mellitus type 2 (V3) in dependence of baseline clinical characteristics. According to concurrent Guidance for Industry for Diabetes Mellitus primary endpoint analysis (change from baseline in glycosylated hemoglobin (HbA1c) level on Vipidia® therapy (V3) in subgroups with different baseline clinical characteristics) should account for factors with substantial correlation with the outcome and independence from the treatment (e.g. prior therapy of DM, sex, age group, cardiovascular risk group, therapy type (monotherapy or combined therapy) etc.).

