9.1. Statistical Analysis of the Primary Efficacy Variable(s)

Primary study outcome - change from baseline in glycosylated hemoglobin (HbA1c) level on Vipidia® therapy (V3). Taking into account inclusion criteria (either newly diagnosed DM type 2 (drug naive) or inadequate glycemic control on previously prescribed any oral antidiabetic drug) as well as non-intervention nature of the study it is proposed to use multifactorial regression model to determine factors related to effect of Vipidia® on glycosylated hemoglobin (HbA1c) level dynamics.

Change from baseline in glycosylated hemoglobin (HbA1c) level on Vipidia® therapy (V3) in subgroups with different clinical characteristics will be summarized using relevant descriptive statistics and analyzed using Multiple Linear Regression with following predictors: prior therapy of DM, sex, age, cardiovascular risk group, therapy type (monotherapy or combined therapy), baseline BMI, initial glycemic control, T2DM duration. No subgroup analyses will be performed within interim analysis of study data.

In addition, change from baseline in glycosylated hemoglobin (HbA1c) level will be assessed and evaluated using Mixed model repeated measures (MMRM) methodology [14, 15]. The multiple visits for each patient will be incorporated as repeated measures within each patient. Visit will be treated as a categorical predictor and baseline glycosylated hemoglobin (HbA1c) level and duration of T2 DM will be included as a covariate. An appropriate covariance structure will be selected to provide estimates (Least Square Means) of change from Baseline and to perform statistical analysis at Visit 3. The dose-response trend hypothesis test will be conducted using the appropriate contrast statement for a linear (ordinal dose) trend. In addition, Least Squares Means, the associated standard errors and 95% confidence intervals will be displayed by each individual dose group.

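### SAP 9.1: the Visit 3 Least Squares Mean with baseline HbA1c as a fixed covariate gives too narrow an interval for the mean HbA1c change in a study without a comparator, and can be biased if dropout depends on HbA1c

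*SAP*

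**What the plan says.** Section 2.1 describes the design: "This is a local, prospective, multicentre, non-interventional, observational study in adult patients with T2DM diagnosis". No comparator is described. Section 2.4 sizes the study on precision, using "power for Confidence Interval for Paired Mean Difference as for accuracy of parameter estimation", with "Correlation 0.35", an SD of at most 0.70 and half-widths from 0.05 to 0.10.

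Section 9.1 first gives a multiple linear regression to find factors related to the change. It then adds an MMRM of change from baseline, with visit as a categorical predictor, in which "baseline glycosylated hemoglobin (HbA1c) level and duration of T2 DM will be included as a covariate". The model is there "to provide estimates (Least Square Means) of change from Baseline and to perform statistical analysis at Visit 3". On intervals, 9.1 says that "Least Squares Means, the associated standard errors and 95% confidence intervals will be displayed by each individual dose group". It does not say at which baseline value the Least Squares Mean is evaluated.

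Three other provisions bear on the point. HbA1c change is also summarised descriptively (sections 3 and 9). The closing paragraph of 9.2 adds paired t or Wilcoxon tests for variables that are changes between visits. Section 5 assumes data missing at random without imputation, and requires three sensitivity analyses, one of them regression imputation, if more than 1% of outcomes are missing.

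**The concern.** In a two-arm comparison, the sampling error of the mean baseline cancels from the difference between adjusted means. Without a comparator, nothing cancels it. The MMRM interval then describes the mean change for patients with this sample's average baseline, while section 2.4 sizes the study for the unconditional mean change. Read as the latter, the interval is too short.

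The second issue is missing data. Because baseline is a covariate and not an outcome, a patient with no post-baseline HbA1c contributes no record. The usual default evaluates the Least Squares Mean at the mean baseline of the records that remain. If patients with higher HbA1c leave more often, that mean is too low and the estimated fall is too small, even though the data are missing at random. At stake is the model-based figure for the primary endpoint. The interim analysis of 350 patients uses the same methods, and its results are to be made public.

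**Working it through.** **1. The plan's own figure.** Inputs from section 2.4: SD 0.70, correlation ρ = 0.35, two-sided alpha 0.05, conditional probability of width 0.9, half-width 0.05.
- SD of change = 0.70 × √(2(1 − 0.35)) = 0.70 × √1.30 = 0.798.
- The exact t-interval calculation gives 1037 pairs (probability 0.900), as stated. Four other table rows checked (770, 899, 313, 275) also reproduce.
- 1037 / 0.75 = 1382.7, so 1383 enrolled, as stated.

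The table therefore treats 0.70 as the SD of each measurement and targets the unconditional mean change.

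**2. Whole-cohort coverage.** Take equal SDs σ at V1 and V3.
- Slope of change on baseline: ρ − 1 = −0.65.
- Variance in the model SE: σ²(1 − ρ²)/n = 0.49 × 0.8775/n.
- Variance omitted, from the sample mean baseline: σ²(1 − ρ)²/n = 0.49 × 0.4225/n.
- Sum: 0.49 × 1.30/n, which is the paired-difference variance of step 1.
- SE ratio = √(0.8775/1.30) = √((1 + ρ)/2) = √0.675 = 0.822.
- Coverage = 2Φ(1.96 × 0.822) − 1 = 89.3%.
- At n = 1037 the half-width is 0.040 instead of 0.049.

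A simulated MMRM with complete data (n = 1037) gave 89.3%, and the paired t interval 94.9%. The ratio depends on neither σ nor n. Other inputs give:

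| Input changed | Coverage |
|---|---|
| ρ = 0.2 | 87.1% |
| ρ = 0.5 | 91.0% |
| ρ = 0.7 | 92.9% |
| V3 SD / V1 SD = 0.8 (ρ = 0.35) | 84.3% |
| V3 SD / V1 SD = 1.25 (ρ = 0.35) | 92.3% |

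With 25% dropout completely at random, all after V2, simulated coverage was 90.5%. T2DM duration is left out of this working. If it predicts change beyond baseline HbA1c, it shortens the model SE further.

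**3. Dose-group coverage.** For a group holding a share p of patients, evaluated at the overall mean baseline, the squared SE ratio is (1 + ρ)/((1 + ρ) + p(1 − ρ)).
- p = 0.8: 1.35/1.87 = 0.722, coverage 90.4%.
- p = 0.5: 1.35/1.675 = 0.806, coverage 92.2%.
- p = 0.1: 1.35/1.415 = 0.954, coverage 94.4%.

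The SAP gives no dose split. The dose-trend contrast is not affected in this way, because the common mean baseline cancels.

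**4. Bias under HbA1c-dependent dropout.** The following are assumptions, not SAP figures: the dropout slope, a V2–V3 correlation of 0.6, a V1–V2 correlation of 0.35, and evaluation at the mean baseline of retained records. The table is for n = 1383, 25% dropout, and log-odds of 0.5 and 1.0 per SD.

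| Dropout depends on | MMRM bias | MMRM coverage | Paired-mean bias |
|---|---|---|---|
| Baseline, before V2 | +0.054 / +0.098 | 28% / 1% | +0.054 / +0.098 |
| Baseline, after V2 | +0.023 / +0.041 | 75% / 46% | +0.054 / +0.097 |
| V2 value, after V2 | +0.009 / +0.015 | 89% / 81% | −0.021 / −0.036 |
| Mixed, before and after V2 | +0.033 / +0.058 | 60% / 21% | +0.015 / +0.025 |

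The first row shows the mechanism: 0.054/0.65 = 0.083, so the retained patients' mean baseline is about 0.083 points too low. Two further simulations of 1403 patients, with dropout on the last HbA1c at log-odds 0.25, 0.5 and 0.8, gave +0.017, +0.033, +0.054 and +0.021, +0.038, +0.065. In the first of these the V1–V2 correlation was 0.5.

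Evaluating at the mean baseline of all enrolled patients cut the bias to about 0.001 in the tabulated settings. In a mixed setting with V1–V2 correlation 0.5, it fell from 0.037 to 0.006. Coverage stayed at about 89% to 92%.

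**5. V1, V2 and V3 as outcomes.** The V3-minus-V1 contrast had bias below 0.001 and coverage of 94% to 95%, with complete data and under the first three mechanisms at log-odds 1.0. A separate run of 1403 patients gave bias of at most 0.003 and a half-width of about 0.046.

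**The case against.** A reader might infer that the primary endpoint will be reported with an 89% interval around a biased estimate. The document does not support that.

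- It writes out 95% intervals only by dose group. A whole-cohort interval is a reasonable inference from the plan to analyse Visit 3, but it is not stated, and smaller dose groups lose less coverage.
- The MMRM is an addition. The descriptive summaries and paired tests match the quantity sized in section 2.4, and the paired interval has nominal coverage when dropout is uninformative.
- At the planned 25% dropout, the sensitivity analyses of section 5 are triggered. Regression imputation can use the baseline values of patients who have no later HbA1c.
- A baseline-adjusted interval is valid given the observed baselines. The study is descriptive, and no margin or decision hangs on a difference of about 0.009 in half-width (0.049 − 0.040).

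All of this stands and lowers the severity. It does not remove the point. The MMRM is the only analysis in 9.1 that says how the Visit 3 change is estimated with a standard error and interval, and nothing labels that interval as conditional on baseline. The paired tests come without a stated interval. The sensitivity analysis covers the bias only in part and leaves the MMRM standard error as it is.

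It would also go too far to say that the MMRM is more biased than the paired mean. In the table it is worse under mixed dropout, equal when dropout depends on baseline before V2, and better when it depends on baseline after V2. For dropout on the V2 value, the order depends on the assumed V1–V2 correlation: with 0.5 in place of 0.35 and log-odds 0.5, the biases were +0.014 for the MMRM and −0.009 for the paired mean.

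**Conclusion.** The point holds in two parts of unequal strength.

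**Coverage (high confidence).** As an interval for the mean change, the nominal 95% Least Squares Mean interval covers about 89% for the whole cohort. This rests on the SAP's correlation of 0.35, equal SDs, and the unconditional mean change as target. Over correlations 0.2 to 0.7 the range is 87% to 93%. For dose groups it is about 90% to 94%, depending on the group's share of patients.

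**Bias (medium confidence).** If the mean is evaluated at the retained records, which is the usual default and which the SAP does not override, HbA1c-dependent dropout biases Visit 3 even under the MAR assumption of section 5. The size was roughly +0.01 to +0.07 points in most settings at log-odds up to 0.8 per SD, and up to about +0.10 at log-odds 1.0 on baseline before V2. The target half-width is 0.05. The mechanism is certain; its size in this study is not known.

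This should be fixed, but it does not invalidate the primary analysis.

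**What to change.** In 9.1, fit HbA1c at V1, V2 and V3 as repeated outcomes for all enrolled patients with a baseline value, with categorical visit and an unstructured covariance. Report the V3-minus-V1 contrast with its 95% CI as the model-based mean change.

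If the baseline-adjusted Least Squares Mean is kept, label its interval as conditional on the observed baselines and evaluate it at the mean baseline of all enrolled patients. That removes most or all of the bias under MAR but leaves the shortfall in coverage.

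The cost is SAP wording and a few lines of code. The printed interval becomes about 17% wider, with a half-width of about 0.046 against 0.039. As a check, the simulated SE ratios with dropout are 0.0237/0.0203 = 1.17 and 0.0231/0.0196 = 1.18. The half-width remains inside the 0.05 target, so the sample size need not change.

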5. STATISTICAL / ANALYTICAL ISSUES

Visit windows

In accordance with the protocol, due to the non-interventional study design it's not possible to appoint exact times for the study visits, although it is expected that the period of observation will be approximately 6 months. The frequency of the visits will be assigned by each physician according to their routine practice. It is anticipated that the patients will visit their physician every 3 months and more often at the beginning.

So, for the analysis and summary of clinical laboratory, efficacy, and safety data in case of this analysis/summary performed on "by visit" base. In the event of multiple values for an assessment within an analysis window, the value closest to the scheduled visit date will be used for analyses. If two values tie as closest to the time point (for example, one value is before and the other value is after the time point), then the later value will be selected as the analysis value.

Analysis Window	Start	End	Target	Assessment to be used if duplicates
Baseline visit	<1			NA
Month 3 (Visit 2)	0	135	90	Closest to target day, if equidistant use later result.
Month 6 (Visit 3)	136	NA	180	

The definition for the study days included in each study window is defined as below:

Treatment Day prior to first dose = Visit Date – Date of First Dose

Treatment Day on or after first dose = Visit Date – Date of First Dose + 1

Adjustments for Covariates

No specific adjustments for covariates will be made in all statistical analyses, unless specified otherwise per-analysis level.

Handling of Dropouts or Missing Data

Missing efficacy outcomes will be assumed to be missing at random (MAR) and thus will not be imputed in the primary analysis. However if greater than 1% of all primary/secondary outcomes that should be available for analysis are missing, a sensitivity analysis will be undertaken in addition to the primary MAR analysis.

This sensitivity analysis will include an evaluation of the results of models developed under the assumptions of:

- 1) last observation carried forward;
- 2) worst extreme case imputation and;
- 3) regression model imputation using all available information.

Outlier identification

During data Quality Control outlier identification will be performed using adjusted Z-score method (Iglewicz and Hoaglin, 1993).

$$M_i = \frac{0.6745(x_i - \bar{x})}{MAD}$$

where MAD - Median absolute deviation, \bar{x} - median.

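### The section 9.1 MMRM for the V3 HbA1c change omits prior therapy and therapy type, so its missing-at-random assumption is weaker than it need be and the V3 mean may be biased

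*SAP*

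**What the plan says.** Section 9.1 plans two models for the change in HbA1c. The first is a regression to find factors related to response, "analyzed using Multiple Linear Regression with following predictors: prior therapy of DM, sex, age, cardiovascular risk group, therapy type (monotherapy or combined therapy"). Its other predictors are diabetes duration, BMI at baseline and the initial level of glycaemic control. The second is introduced with "In addition, change from baseline in glycosylated hemoglobin (HbA1c) level will be assessed and evaluated using Mixed model repeated measures (MMRM) methodology". For that model "The multiple visits for each patient will be incorporated as repeated measures within each patient", visit is categorical, and "baseline glycosylated hemoglobin (HbA1c) level and duration of T2 DM will be included as a covariate". It is the only 9.1 model said to yield least squares means and the analysis at V3. A dose term is implied by the trend contrast in the same paragraph, but no therapy term is named.

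Section 5 (Adjustments for Covariates) sets the default: "No specific adjustments for covariates will be made in all statistical analyses, unless specified otherwise per-analysis level". The 9.1 list is therefore the whole list unless the SAP is changed. Section 5 (Handling of Dropouts or Missing Data) assumes missing at random with no imputation in the primary analysis. It adds sensitivity analyses, one of them a regression imputation from all available data, if more than 1% of outcomes are missing.

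Section 2.4 says that the analysis of V3 change in subgroups "should account for factors with substantial correlation with the outcome and independence from the treatment", and gives prior therapy and therapy type among its examples. The paragraph opens with "As well as for the primary objective, sample size was calculated for the secondary objective of the study".

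**The concern.** In a likelihood-based repeated-measures model, missing at random is conditional on what the model contains: its covariates and the observed outcomes. The SAP enrols drug-naive patients together with patients inadequately controlled on an oral drug, and gives that mix as its reason for a multifactorial regression. The same mix bears on the MMRM. If pretreated patients have a smaller HbA1c fall and also leave more often, the patients seen at V3 over-represent the better responders. A model without therapy corrects for this only as far as baseline HbA1c, diabetes duration and V2 carry the information. What is at stake is the model-based estimate of the primary endpoint, in a study sized for precision rather than for a test, with a quarter of patients expected to drop out.

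**Working it through.** **The plan's own figures.** Inputs from section 2.4: SD 0.70, correlation 0.35, half-width 0.05, two-sided alpha 0.05, probability of achieving the width 0.9.
- SD of the paired difference = 0.70 × √(2 × (1 − 0.35)) = 0.798.
- The exact calculation, conditional on coverage, gives 1037 pairs with probability 0.900, as the SAP states.
- Enrolment for 25% dropout: 1037 / 0.75 = 1383, as stated. The regression figure is 1052 / 0.75 = 1403, also as stated.

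The yardstick for any bias is therefore the half-width of 0.05.

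**Bias before V2 data help.** The only input from the SAP is the 25% overall dropout. Assumed: prior-therapy mix 30/50/20%, with the V3 changes and dropout rates shown. Completer share of a group = share × (1 − dropout) / 0.75.

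| Scenario | V3 changes | Dropout | Enrolled mean | Completer shares | Completer mean | Bias |
|---|---|---|---|---|---|---|
| Mild | −1.0/−0.8/−0.7 | 20/25/32.5% | −0.840 | 32/50/18% | −0.846 | −0.006 |
| Middle | −1.2/−0.8/−0.6 | 15/25/40% | −0.880 | 34/50/16% | −0.904 | −0.024 |
| Strong | −1.3/−0.8/−0.5 | 10/25/47.5% | −0.890 | 36/50/14% | −0.938 | −0.048 |

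**Bias of the MMRM as specified.** Observed V2 values recover part of this. The scenarios were simulated with 1403 enrolled, residual SD 0.75 and V2–V3 correlation 0.6 (both assumed), with dropouts split 50/50 or 80/20 before and after V2.

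| Scenario | Bias | Share of 0.05 | 95% CI coverage |
|---|---|---|---|
| Mild | about −0.003 | 6% | not material |
| Middle | −0.016 | 32% | about 90% |
| Strong | about −0.03 | 60% | about 73–75% |

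Coverage = Φ(1.96 − b/SE) − Φ(−1.96 − b/SE). A ratio b/SE of 0.67 gives 0.90, and 1.34 gives 0.73. With prior therapy added, bias is 0.005 or less throughout, and the SE is about 0.023 against 0.023–0.024 without it.

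Varying the share of dropouts who leave before V2 from 20% to 80%, and assuming that V2 shows 80% of the V3 change, gives −0.003 to −0.005, −0.013 to −0.021, and −0.027 to −0.042.

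**Which conditions are needed.** A two-group, large-sample check assumed therapy share 50%, 25% overall dropout, correlation 0.6 and a V2 difference equal to 70% of the V3 difference.

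| Dropout gap | V3 difference | No V2 for dropouts | MMRM as specified | With therapy |
|---|---|---|---|---|
| 10 points | 0.3 | −0.010 | −0.006 | 0.000 |
| 20 points | 0.3 | −0.020 | −0.011 | 0.000 |
| 30 points | 0.5 | −0.049 | −0.027 | 0.000 |
| 0 | 0.5 | 0.000 | 0.000 | 0.000 |
| 30 points | 0 | 0.000 | 0.000 | 0.000 |

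The last two rows show that both links are needed: therapy must relate to dropout and to V3 change given the model terms.

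**The case against.** A reader might infer that 9.1 contradicts section 2.4. It does not. The 2.4 sentence stands under the secondary objective and defines its analysis as change in subgroups. The sample size that follows it is for a multiple linear regression, and 9.1 supplies that regression with every factor 2.4 names. Calling it a primary endpoint analysis is loose wording and does not place a requirement on the MMRM. What 2.4 does show is that the SAP regards these factors as predictive of outcome.

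A reader might also infer that the V3 mean is biased whenever dropout differs by therapy. That does not follow, as the zero rows show. The SAP gives no rates by therapy, so neither the presence nor the direction of a bias is known.

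The other objections have weight:
- Section 9.2.1 fits a mixed model to the same HbA1c changes with clinical characteristics as factors. With 25% dropout planned, the regression imputation will almost certainly be triggered. But 9.2.1 is secondary, does not name its characteristics and specifies no V3 least squares mean. The imputation is only a sensitivity analysis. Neither replaces the 9.1 estimate.
- Duration is already in the model and partly stands in for prior therapy, since drug-naive patients are described as newly diagnosed. Assuming mean durations of 0.5, 5 and 8 years by group, the three scenario biases fell from −0.004 to −0.003, −0.017 to −0.011, and −0.035 to −0.022, roughly a third less in the two larger cases.
- The study is descriptive, and 0.03 is a tenth of the SAP's 0.3% response cut-off. The consequence is modest in clinical terms. It is less so against the precision for which the study was sized.

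**Conclusion.** The point holds as a weakness in the model specification and not as a demonstrated bias or an internal contradiction. The MMRM that gives the V3 mean leaves out recorded factors that the SAP treats as outcome-related, and so relies on a stronger missing-data assumption than necessary. The possible bias ranges from zero or about 0.003 to about 0.03 HbA1c points, and up to 0.04–0.05 in the strongest assumed cases when most or all dropouts lack a V2 value. These sizes rest on assumed therapy mixes, responses, dropout rates and correlation; only the 25% dropout and the 0.05 half-width come from the SAP. The upper figures need large differences between therapy groups in both response and dropout. The change is worth making because it is cheap and showed no loss of precision in the simulation.

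**What to change.** In the 9.1 MMRM, add prior diabetes therapy and therapy type as recorded at baseline, each with a visit interaction. Name both in the text so that the section 5 default does not exclude them. Report the V3 least squares mean at the observed margins of the enrolled population. Equal-weight margins would describe a population with equal shares in every therapy category, which is not the one enrolled. The simulations tested only a prior-therapy or single therapy factor, so they give no evidence for adding the whole regression list.

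The cost is a change of SAP wording and of one model statement, using variables already listed for 9.1. The model gains a few parameters. It also needs a stated rule for patients who lack a predictor, so that they are not silently dropped. A separate missing category is one option, but it can itself distort adjustment in observational data and should be justified if used.
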